7.2. Screening and Critical Baseline Assessments

Before any study-specific procedure is performed, valid informed consent must be obtained.

Demography and medical history (including cardiovascular medical history/risk factors, T2DM history, history of other prior and concomitant medical conditions) will be assessed at screening (as detailed in the eCRF).

Critical baseline assessments will include: GEBT, EGG.

Full details of screening and baseline assessments are provided in the Time and Events Table Section [7.1](#).

7.3. EGG and GEBT Test

GEBT and EGG measurements will be undertaken in the clinic and performed on separate days. Measurements for both Part A and Part B will be taken at the time points specified in the Time and Events Table in Section [7.1](#). Clinical visits for EGG and GEBT will have a visit window of ± 1 day and should be planned to avoid days of expected holidays, weekends and vacations.

- Albiglutide should be self-administered in the morning 3 ± 1 days before the EGG procedure.
- Exenatide should be self-administered twice daily. In the morning of each test day, subjects should be instructed NOT to self-administer exenatide at home. The morning dose of exenatide on the day of in-clinic test must be administered by the site staff. The dose of exenatide should be administered 1 hr ± 15 min prior to the start of the EGG or GEBT procedure. Every effort should be made to administer at the same pre-procedure time at each visit for the same subject.

7.3.1. EGG

Subjects should have nothing to eat or drink from midnight prior to the EGG. Two hours before the EGG subjects will be provided one piece of toast and 4 US fluid ounces (120 mL) of apple juice. This provides a small amount of calories so subjects are not “starving” and also provides a consistent EGG baseline before the water load. Subjects should not have anything further to eat or drink until after the EGG procedure.

EGG is recorded with ECG-type electrodes placed on the surface of the epigastrium. The EGG signals are recorded on a strip chart for visual analysis and digitized simultaneously for computer analysis. The EGG recordings include a 15-min baseline tracing after which the subjects ingest water for 5-min until they perceive their stomach is full. All subjects will rate symptoms experienced immediately before and 10, 20 and 30 min after ingestion of the water.

A VAS (0-100 mm) will be used to assess the intensity of the following sensations: no nausea (0) to severe nausea (100), stomach empty (0) to stomach full (100), hunger (0) to

satiety (100) and no bloating (0) to severe bloating (100). The recording channel with the clearest electrogastrographic signal will be chosen for visual and computer analysis.

The details of test procedures for EGG with water load test are provided in the SRM.

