In a head to head, 32-week, open-label clinical trial in patients with T2DM, in which non-inferiority of albiglutide of a 95% confidence interval (CI) upper margin of 0.3% for HbA_{1c} was not met, the incidence of nausea was 9.9% for albiglutide and 29.2% for liraglutide, and the incidence of vomiting 5.0% and 29.3% respectively [Pratley, 2014]. In a 26-week open-label, forced titration clinical trial, nausea was reported in approximately 25.5% and 28% of subjects treated with liraglutide and exenatide, respectively [Buse, 2009]. In exenatide Phase 3 program, nausea was reported in up to 44% of subjects receiving exenatide [Byetta, US Prescribing Information, 2015]. Dulaglutide, another once weekly GLP-1R agonist reported ~20% incidence of nausea at the highest approved dose in the results from pooled placebo-controlled trials [Trulicity, US Prescribing Information, 2015].

The reasons for the differences in incidence of nausea in clinical trials between albiglutide and other GLP-1R agonists are not fully understood. Potential explanations include differences in the pharmacokinetic profiles (e.g., albiglutide T_{max} ~3 days, dulaglutide T_{max} ~2 days, exenatide T_{max} ~2.1 h, or liraglutide T_{max} ~13h). It is unknown if these differences result in compound specific patterns of receptor occupancy and pharmacodynamic response. Differences in molecular size and structure among GLP-1R agonists may also impact penetration through the blood brain barrier and activity in brain receptors.

Electrogastrogram (EGG) is a noninvasive technique to assess GMA [Koch, 2001]. It is used in clinical practice to identify if patients with nausea and other upper GI symptoms without mechanical causes have disturbances in the myoelectrical gastric rhythm, and to confirm the diagnosis of gastroparesis. “EGG with water load test” is a standardized test to induce gastric distention and measure myoelectrical responses as well as collect VAS of upper gastrointestinal symptoms (stomach fullness, hunger, nausea, bloating and abdominal pain) under standardized conditions. The gastric distention produced by the water load induces nausea in a high proportion of patients, allowing the assessment of GMA during the episodes of nausea. Episodes of nausea are typically associated with disturbance in GMA called gastric dysrhythmias.

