3.2. Part B: Objectives and Endpoints

Objectives	Endpoints
Primary	
To evaluate the effect of albiglutide on GMA compared to exenatide	
 • Change from baseline in EGG parameters at Weeks 2, 5, and 8 at each time interval (pre-and 10, 20 and 30 min after water load) • Distribution of average power by frequency region (as % of power) • Ratios of average power post-WLT/pre-WLT by frequency region • Percentage (%) of time with the dominant EGG frequencies in the four frequency ranges (bradygastria, normal, tachygastria and duodenal) • Change from baseline in EGG parameters related to VAS of nausea at Week 2, 5, and 8 at each time interval (pre-and 10, 20 and 30 min after water load)
Secondary	
To assess the effect of albiglutide on GE compared to exenatide	
 • Change from baseline of time to half gastric emptying (GE$1\frac{1}{2}$) at Weeks 5 and 8 • Change from baseline of profiles of ^{13}C excreted in breath (kPCD1) at Weeks 5 and 8 and at each time interval (45, 90, 120, 150, 180 and 240 min)

Objectives	Endpoints
To assess the effect of albiglutide on the volume of water ingested during EGG compared to exenatide	Change from baseline of volume of water ingested during water load EGG test at, Weeks 2, 5 and 8.
To evaluate the effect of albiglutide on stomach fullness, hunger, bloating and abdominal pain during EGG with water load test compared with exenatide	Change from baseline of VAS of stomach fullness, hunger, bloating and abdominal pain during the EGG water load test at each time interval (pre-and 10, 20 and 30 min after water load) at Weeks 2, 5, and 8.
To evaluate safety and tolerability of albiglutide and exenatide	
 • Vital signs, clinical laboratory tests, AEs, and GCSI-DD. • Nausea AEs presenting outside the timing of the WLT and GCSI-DD.
Exploratory	
To evaluate change in gastric rhythm status (Data permitting)	
 • At Weeks 2, 5, and 8; over 30 min and at each time interval (pre-and 10, 20 and 30 min after water load). 
 • Number and % of subjects with a shift in gastric rhythm status. • Number and % of subjects by gastric rhythm status. • Mean and mean change from baseline in average dominant frequency

1. Percent dose excreted of ^{13}C *1000

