6.10.1. Permitted Medications and Non-Drug Therapies

Unless specified as a prohibited medication in Section 6.10.2, all concomitant prescription or over the counter medications should be considered permitted provided they are not contraindicated in the albiglutide or exenatide (depending on study treatment) PI or for the individual subject concerned. Although stable doses of all concomitant medications are preferable, changes in medications during the study to appropriately treat clinical conditions that might arise are allowed.

Like other members of the class, albiglutide and exenatide cause a delay in gastric emptying, and thereby have the potential to impact the absorption of concomitantly administered oral medications. This should be taken into account by investigators when prescribing concomitant medication.

Investigators must adhere to the US FDA-approved PI for all permitted medications.

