9.2.4. Key Elements of Analysis Plan

9.2.4.1. Primary Analysis

The primary endpoint is change from baseline in EGG parameters at Week 2, 5, and 8 at each time interval (pre-and 10, 20 and 30 min after water load). The primary endpoint is change in GMA as assessed by EGG parameters: change from baseline of distribution of average power by frequency region (as % of power); change from baseline of ratios of average power post-water load test (post-WLT)/pre water load test (pre-WLT) by frequency region; and change from baseline of percentage (%) of time with the dominant EGG frequencies in the four frequency ranges (bradygastria, normal, tachygastria and duodenal). The primary analyses of the primary EGG parameters will be conducted using mixed-effect model with repeated measures (MMRM). The MMRM model will include the EGG parameter as the dependent variable; treatment group, time interval, visit week, and treatment-by-week interaction as fixed effects; the relevant parameter baseline as covariate; and subject as a random effect.

The primary endpoint of change from baseline in EGG parameters related to VAS of nausea at Week 2, 5, and 8 at each time interval (pre-and 10, 20 and 30 min after water load) will be analyzed using the MMRM method as described above. The MMRM model will include the EGG parameter as the dependent variable (the same EGG parameters as listed above); treatment group, time interval, visit week, and treatment-by-week interaction as fixed effects; the relevant parameter baseline as covariate; VAS of nausea as time varying covariate; and subject as a random effect.

Treatment effects estimates (and associated 95% CI) of albiglutide will be evaluated within this MMRM model as least squares means contrasts relative to exenatide. An unstructured covariance matrix will be used for the MMRM analysis, unless the model does not converge, in which case the covariance matrix will be decided upon model convergence status and the Akaike information criterion.

Part B analysis is further described in the RAP.

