9.2.4.2. Secondary analyses

The relative effects of albiglutide compared to exenatide will also be assessed across a number of secondary endpoints. The secondary endpoints are defined in Section 3.2 and include change from baseline in $T_{1/2}$ at Week 5 and 8; change from baseline in kPCD of GE at Week 5 and 8 and at each time interval (45, 90, 120, 150, 180 and 240 min); change from baseline volume of water ingested during water load EGG test Week 2, 5 and 8; and change from baseline of VAS of stomach fullness, hunger, bloating and abdominal pain during the EGG water load test at Week 2, 5, and 8. The secondary endpoints will be analyzed analogous to the primary endpoint using MMRM. In addition, summary statistics (including number of subjects, mean, median, min, max, SD, SE) and graphical displays will be provided.

The overall general safety and tolerability of albiglutide versus exenatide will be evaluated in tabular and/or graphical format and summarized descriptively.

Vital signs, clinical laboratory tests, adverse events (AEs), Gastroparesis Cardinal Symptom Index – Daily Diary (GCSI-DD), and nausea AEs presenting outside the timing of the WLT and GCSI-DD will be assessed using descriptive statistics.

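### Subjects drink water until full, so the planned post-load contrasts estimate a total drug effect at a self-chosen load, and the model does not isolate the load-free interval

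*Protocol*

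**What the plan says.** **The load.** Protocol section 2.1 says the EGG with water load "is a standardized test to induce gastric distention and measure myoelectrical responses". Section 7.3.1 describes a 15-minute baseline tracing, "after which the subjects ingest water for 5-min until they perceive their stomach is full". It states no fixed, minimum or maximum volume and leaves further procedure to the Study Reference Manual. Symptoms are rated just before drinking and at 10, 20 and 30 minutes after it.

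**The load can affect the outcomes.** Section 2.1: "The gastric distention produced by the water load induces nausea in a high proportion of patients".

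**The drugs can affect the load.** Section 6.10.1 says that "albiglutide and exenatide cause a delay in gastric emptying". Section 3.2 has a secondary objective: "To assess the effect of albiglutide on the volume of water ingested during EGG compared to exenatide". Section 9.2.4.2 models "change from baseline volume of water ingested during water load EGG test Week 2, 5 and 8".

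**The models.** Section 9.2.4.1 gives the primary mixed model as "treatment group, time interval, visit week, and treatment-by-week interaction as fixed effects; the relevant parameter baseline as covariate; and subject as a random effect". The model for EGG parameters related to nausea adds only "VAS of nausea as time varying covariate". Secondary endpoints, including the symptom scales, follow the same form. No model contains volume, and none crosses treatment with time interval, although the primary endpoint is defined at each interval.

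**Part A.** Section 4.2 makes progression depend on a detectable change in gastric myoelectrical activity caused by exenatide. The SAP covers Part A only and, after early termination, replaces analysis of the exploratory endpoints with listings (sections 2.1 and 7.1).

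**The concern.** Section 4.4 says the study is meant to learn whether a peripheral gastric mechanism explains the difference in tolerability between the two drugs. Drinking to fullness equalises a perception, not a volume. If one drug makes subjects stop sooner, the later EGG power, rhythm percentages, post/pre power ratios and symptom scores follow a smaller stimulus in that arm. A difference between arms could then come from the drug acting on gastric rhythm, from less distension, or from both. The two routes could also cancel.

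The interval before drinking is free of the current visit's load, so it is the cleanest place to look for a direct effect. The planned model does not estimate a separate treatment contrast there.

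In Part A the same ambiguity applies within subject. If intake on Day 4 differs from Day 1, a change in the post-load EGG cannot be read without the change in volume.

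**Working it through.** **1. The plan's own figure.** Sections 4.3.3 and 9.2.2.1 randomise 62 to leave about 50 evaluable (25 per arm) at 20% withdrawal. Forward: 50 / (1 − 0.20) = 62.5. Backward: 62 × 0.80 = 49.6. The figure reproduces and is not in dispute. The size rests on feasibility; no effect size, SD, power or alpha is stated.

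**2. What the listed model estimates.** With treatment and treatment-by-week as the only treatment terms, the contrast in a given week is the treatment coefficient plus that week's interaction coefficient. It takes the same value at every interval.

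| Interval | Current load present? | Contrast in listed model |
|---|---|---|
| Pre-load | No | Common weekly value |
| 10, 20, 30 min | Yes | Same common weekly value |

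Suppose a parameter is measured at all four intervals, the load shifts each post-load contrast by δ, and the pre-load contrast is zero. With equal weights the common contrast shifts by (0 + 3δ) / 4 = 0.75δ, so the load-free and load-exposed intervals are blended. Post/pre power ratios have no pre-load value, so they carry the full δ.

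**3. Illustrative size of δ at one post-load interval.** These inputs are assumptions, because the documents give none:
- ΔV, the between-arm difference in volume: 0.3 to 1.0 SD
- r, the correlation of volume with the post-load outcome: 0.2 to 0.5
- two-sided 0.05, matching the planned 95% intervals

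With no drug effect at equal load, δ = r × ΔV. For a two-sample t-test with 25 per arm, SE = √(2/25) = 0.283 SD, the degrees of freedom are 48, and the noncentrality is δ / 0.283.

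| r | ΔV (SD) | δ (SD) | δ / SE | Rejection |
|---|---|---|---|---|
| any | 0 | 0 | 0 | 5.0% |
| 0.2 | 0.3 | 0.06 | 0.21 | 5.5% |
| 0.3 | 0.8 | 0.24 | 0.85 | 13% |
| 0.5 | 0.8 | 0.40 | 1.41 | 28% |
| 0.5 | 1.0 | 0.50 | 1.77 | 41% |

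For scale, the difference detectable with 80% power is 0.81 SD. By step 2, a contrast pooled over four intervals would shift by 0.75 × 0.06 = 0.045 SD to 0.75 × 0.50 = 0.375 SD.

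**4. Masking.** A direct effect of +0.40 SD with slope −0.5 and ΔV = 0.8 gives 0.40 − 0.5 × 0.8 = 0. Simulation agreed (mean contrast −0.002 SD).

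**5. Does adjusting for volume settle it?** Simulation, 5,000 runs per scenario, 25 per arm, slope 0.5, ΔV = 0.8, no direct effect:

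| Scenario | Unadjusted: mean, rejection | Adjusted for volume: mean, rejection |
|---|---|---|
| No common cause of volume and outcome | 0.40 SD, 28% | 0.00 SD, 5% |
| Unmeasured common cause | 0.40 SD, 24% | −0.15 SD, 8% |

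The common cause loads 0.6 on volume and 0.6 × 0.5 = 0.3 on outcome. The expected bias is −0.8 × 0.6 × 0.3 = −0.144 SD, in line with the simulation. Adjustment helps, but it is not clean.

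**6. The two SAP copies.** In one copy, section 9.5.3 runs to listing 20: EGG endpoints are listing 16 and ingested volume is listing 20. In the other, section 9.5.1 gives exploratory endpoints only listing 15 (EGG), and section 9.5.3 ends there. Yet section 7.2 of both copies promises listings for all endpoints.

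**The case against.** The strongest reply is that nothing here is an analysis error. Drinking to fullness standardises the perceived endpoint, and the unadjusted randomised contrast is a valid total effect under that test. If a drug lowers intake and the EGG response follows, that is a real consequence of the drug. This stands. A reader might infer that the plan inflates the type I error to as much as 41%. The documents do not support that: they define no effect at equal load, and the rejection rates are false positives only against that target and only under assumed inputs.

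A second reply is that volume is measured after randomisation and lies on the causal path, so adjusting for it can introduce bias. This also stands (step 5). It would be tempting to credit a direct effect only when the difference survives adjustment, but the adjusted model cannot act as such a gate. Nor is the nausea covariate a precedent: that model serves a separately listed endpoint.

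A reader might also infer that the fullness score is fixed by design. It is not. Ratings come at 10 to 30 minutes rather than at the moment of stopping, and some subjects may reach the 5-minute limit before they feel full.

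Other replies limit the reach of the point. Volume is compared between arms, so an imbalance would be visible. The Study Reference Manual, not among the documents, may hold volume rules. The protocol defers Part B detail to a later analysis plan. None of this supplies an interval-specific contrast or links volume to the EGG result.

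**Conclusion.** The point holds as a limit on interpretation and a gap in the model, not as a biased analysis. The post-load EGG and symptom contrasts in sections 9.2.4.1 and 9.2.4.2 estimate a total effect at a self-chosen load. They cannot distinguish a direct effect on gastric myoelectrical activity from a smaller stimulus. The missing treatment-by-interval term means the one load-free interval is not shown on its own.

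The size is unknown. The 0.06 to 0.50 SD range depends on the assumed volume difference and correlation, and is zero if mean intake matches between arms. That intake would differ is a possibility the protocol allows for, not a documented fact. Because the study ended early in Part A and the SAP models none of these endpoints, the modelling point concerns the Part B design. Only the Part A listings remain to be acted on.

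**What to change.** **Part B, if it or a similar study is run**
- Keep the unadjusted contrast as the main result and label it a total effect at a self-chosen load.
- For parameters measured at each interval, add treatment-by-interval, crossed with week. Report the pre-load contrast separately from those at 10, 20 and 30 minutes.
- Add a supportive model for post-load EGG and symptom endpoints with volume at that visit and baseline volume as covariates. State that volume is a post-randomisation mediator, that common causes may bias the adjusted estimate, and that it does not decide attribution.
- Print the between-arm volume difference beside each post-load contrast.

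**Part A, now**
- List each subject's Day 1 to Day 4 change in volume beside the EGG change.
- Reconcile the two SAP copies on whether volume is listed.

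**Cost.** Part A needs one listing and a document correction. Part B needs analysis-plan wording, an added interaction and one supportive run per endpoint. Volume is already recorded, and section 4.2 lets statistical refinements after the Part A review go into the analysis plan without a protocol amendment. The price is less precise interval-specific estimates and more results to report at 25 per arm.

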7.3.2. GEBT

The GEBT should be administered after an overnight fast. No solid food should be consumed or vigorous activity undertaken within 8 hours prior to the test. Alcohol should not be ingested within 8 hours prior to testing. The individual being tested may consume a small amount of water up to 1 hour before the test, but not more than 4 fluid ounces. Coffee may enhance gastric motility and should not be consumed within 8 hours prior to testing. Subjects should not smoke/use tobacco products (e.g. chewing tobacco, nicotine gum) before or during administration of GEBT.

The GEBT will be conducted over a four-hour period. After an overnight fast, duplicate pre-meal breath samples will be collected in capped glass tubes. Subjects will then consume a standard GEBT meal containing ^{13}C -Spirulina. Breath samples will be collected periodically. All breath samples pre- and post-meal will be returned to a central laboratory for analysis by Gas Isotope Ratio Mass Spectrometry (GIRMS) to determine the ratio of $^{13}\text{CO}_2/^{12}\text{CO}_2$ in each sample. By measuring the change in this ratio over time as compared to the pre-meal value, the rate of $^{13}\text{CO}_2$ excretion can be calculated and the individual's gastric emptying rate determined.

The details of GEBT administration instructions and breath sample collection procedures will be provided in the SRM.

7.4. Safety

Planned time points for all safety assessments are listed in the Time and Events Table (Section 7.1). Unscheduled visits will occur as medically necessary. Detailed procedures for obtaining each assessment are provided in the SRM.

7.4.1. Adverse Events (AE) and Serious Adverse Events (SAEs)

The definitions of an AE or SAE can be found in [Appendix 6](#).

The investigator and their designees are responsible for detecting, documenting and reporting events that meet the definition of an AE or SAE.

Events of nausea, hunger, stomach fullness, bloating, and abdominal pain resulting from the water load test will be captured and reported as an endpoint through the VAS and will not be considered an AE. Any of these 5 events reported outside of the timings of the VAS collection should be recorded as an AE/SAE if meets the definition as noted in [Appendix 6](#).

7.4.1.1. Time period and Frequency for collecting AE and SAE information

- Any SAEs assessed as related to study participation (e.g., protocol-mandated procedures, invasive tests, or change in existing therapy) or related to a GSK product will be recorded from the time a subject consents to participate in the study up to and including any follow-up contact.
- AEs will be collected from the start of Study Treatment until the follow-up contact (see Section 7.4.1.3), at the timepoints specified in the Time and Events Table (Section 7.1).
- Medical occurrences that begin prior to the start of study treatment but after obtaining informed consent may be recorded on the Medical History/Current Medical Conditions section of the eCRF.
- All SAEs will be recorded and reported to GSK within 24 hours, as indicated in [Appendix 6](#).
- Investigators are not obligated to actively seek AEs or SAEs in former study subjects. However, if the investigator learns of any SAE, including a death, at any time after a subject has been discharged from the study, and he/she considers the event reasonably related to the study treatment or study participation, the investigator must promptly notify GSK.

NOTE: The method of recording, evaluating and assessing causality of AEs and SAEs plus procedures for completing and transmitting SAE reports to GSK are provided in [Appendix 6](#).

